11.2. Sample Size Determination

On the basis of historical data, the TI rate with treatment of best supportive care is expected to be approximately 2.5% in subjects with low or intermediate-1 risk MDS.¹⁷ The primary objective is to evaluate the likelihood that treatment with talacotuzumab or daratumumab can result in a true TI rate $\geq 30\%$. A true TI rate $\leq 15\%$ (6 times of the TI rate of best supportive care) will be considered as of no clinical interest in the context of this Phase 2 study. The number of subjects to be randomized into each arm will be 30, with which the lower boundary of the 2-sided 80% credible interval will exceed 15% if ≥ 8 (26.7%) subjects achieve TI. This sample size determination utilizes a Bayesian approach with $Beta(0.5, 0.5)$ as the prior distribution and $Beta(0.5+m, 0.5+30-m)$ as the posterior distribution for the true TI rate, where m is the observed number of subjects who achieve TI.

11.3. Efficacy Analyses

Primary Endpoint

The primary efficacy endpoint is RBC TI, lasting for at least 8 weeks.

There is no statistical hypothesis testing and no formal statistical comparison between the 2 arms.

Based on the observed number of subjects achieving TI (number of TIs), a Bayesian approach will be used to determine if the outcome of each treatment arm is “meeting” or “not meeting” the primary objective, or statistically “inconclusive.” This statistical assessment will be used to guide decision making for further development of either or both compounds. The evaluation will be performed against the target value (TV) of 30% and the minimum acceptable value (MAV) 15% for the TI rate. The TV of 30% is defined according to study primary objective and is deemed clinically meaningful. A TI rate below 15%, the MAV, will be of no clinical interest. TI rates between MAV and TV will be considered modest, which will define a statistically inconclusive outcome. Operating characteristics (false positive and false negative error rates) of the statistical criteria are calculated using a Bayesian approach with $Beta(0.5, 0.5)$ as the prior distribution and $Beta(0.5+m, 0.5+30-m)$ as the posterior distribution of the true TI rate, where m is the observed number of TIs.

The TI rate point-estimate and corresponding 2-sided 80% credible interval (CI) will also be summarized for each treatment arm.

The above statistical inferences are summarized in the [Table 7](#).

The lower boundary of the 2-sided 80% credible interval will exceed 15% (the MAV) if the observed number of TI is ≥ 8 . If number of TIs is ≥ 13 , then the outcome will be considered highly desirable as the lower boundary of the credible interval will exceed 30% (the TV). If the number of TIs is ≤ 5 , then this will be an undesirable outcome as the upper bound of the credible interval is below 30%. When outcomes are statistically inconclusive (number of TI=6 or 7), results of additional sensitivity analyses and other endpoints (secondary, safety, PK, PD/biomarker) will play a more important role in decision making.

Table 7: Observed TI, 2-Sided Credible Interval, and Statistical Decision Criteria

Number (%) of Observed TI	80% CI ¹	“Meeting” Primary Objective
4 (13.3)	(7.1, 22.9)	No ²
5 (16.7)	(9.6, 26.8)	
6 (20.0)	(12.2, 30.6)	Inconclusive
7 (23.3)	(14.8, 34.3)	
8 (26.7)	(17.6, 37.9)	Yes ³
9 (30.0)	(20.4, 41.4)	
10 (33.3)	(23.3, 44.9)	
11 (36.7)	(26.2, 48.3)	
12 (40.0)	(29.2, 51.7)	
13 (43.3)	(32.3, 55.0)	
14 (46.7)	(35.4, 58.2)	

¹ Using $B(0.5, 0.5)$ as the prior distribution for true IT rate

² With false negative error rate <10%; ie, when observing number of TI ≤ 5 , there is a <10% chance that the true TI rate is $\geq 30\%$

³ With false positive error rate <10%; ie, when observing number of TI ≥ 8 , there is a <10% chance that the true TI rate is $\leq 15\%$

In addition to the aforementioned statistical assessments, sensitivity analyses will also be performed for the primary endpoint. In these analyses, additional subjects will also be considered transfusion independent if they are transfusion-free for less than 8 weeks but have maintained such a status for at least 6 consecutive weeks (42 days) by the time of the clinical cutoff (6 months after last randomization).

Secondary Endpoints

The proportion of subjects with TI lasting at least 168 days (24 weeks), CR, PR, and HI will be summarized descriptively.

The distributions of time to TI, and duration of TI will be estimated for each treatment arm using Kaplan-Meier method. These analyses will be based on subjects who achieve TI.

Other time-to-event endpoints including OS and time to progression to AML will be analyzed using Kaplan-Meier methods.

11.4. Pharmacokinetic Analyses

Data for all subjects who have sufficient and interpretable data for treatment with talacotuzumab or daratumumab will be included in both the PK and the PD analysis. Descriptive statistics (geometric and arithmetic means, standard deviation, and coefficient of variation [%]) will be provided to summarize serum concentrations of talacotuzumab or daratumumab at each sampling time point and PK parameters such as: C_{max} and C_{min} as appropriate.

Pharmacokinetic analyses will be performed on the PK-evaluable population, defined as subjects who have received at least 1 dose of talacotuzumab or daratumumab and have at least 1 postinfusion sample.

All concentrations below the lowest quantifiable concentration or missing data will be labeled as such in the concentration database. Concentrations below the lowest quantifiable concentration will be treated as zero in the summary statistics. The number of subjects and samples excluded from the analysis will be clearly documented in the Clinical Study Report.

Descriptive statistics will be used to summarize talacotuzumab or daratumumab serum concentrations at each sampling time point. C_{\min} is defined as the minimal concentration observed immediately before infusion and C_{\max} is defined as the maximum concentration observed at the end of infusion, as presented in the summary of serum concentration by sampling timepoint. Other PK parameters, if available, may also be summarized.

If sufficient data are available, population-PK analysis of serum concentration-time data of talacotuzumab or daratumumab may be performed and may be combined with data from other studies. If the population-PK analysis is conducted, details will be given in a population-PK analysis plan and the results of the analysis will be presented in a separate report.

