a. To be performed before the start of the infusion.									

TIME AND EVENTS SCHEDULE - DARATUMUMAB PHARMACOKINETICS AND IMMUNOGENICITY ASSESSMENTS

Visit/Timepoint			Daratumumab	
			PK Sample ^{a,b}	ADA (taken from PK sample) ^{a,c}
Cycle 1	Day 1	predose	X	X
		end of infusion	X	
Cycle 2	Day 1	predose	X	X
		end of infusion	X	
Cycle 3	Day 1	predose	X	X
		end of infusion	X	
Cycle 7	Day 1	predose	X	X
		end of infusion	X	
Cycle 12	Day 1	predose	X	X
		end of infusion	X	
Follow-up	4 and 8 weeks after last dose of daratumumab		X	X

ADA=anti-drug antibody, EOT=end-of-treatment, PK=pharmacokinetics

a. Sent to central laboratory.

b. Predose sample to be taken before the start of the infusion (-2 hours) and end of infusion sample to be taken within 2 hours after the end of the infusion. Venous blood samples (5 mL per sample) will be collected for PK/ADA analysis and the serum will be divided into 3 aliquots (1 aliquot for PK analysis, 1 aliquot for antibodies to daratumumab analysis [when appropriate], and 1 aliquot as a backup).

c. An aliquot from the PK sample will be used to assess immunogenicity. A separate blood draw is not needed.

TIME AND EVENTS SCHEDULE – DARATUMUMAB - TABLE FOLLOWING AMENDMENT 4

PHASE
NOTE: After the end of study data collection, subjects who are deriving benefit may continue receiving daratumumab treatment, and will be monitored for serious adverse events that occur during treatment through resolution and entered only into the company safety repository as described under Amendment 4. These subjects will continue to be followed by the study physician according to local standard of care practices and in accordance with daratumumab dosing guidelines.

ABBREVIATIONS

ADA	anti-drug antibody
ADCC	antibody-dependent cell-mediated cytotoxicity
AE	adverse event
AML	acute myeloid leukemia
ANC	absolute neutrophil count
ALT	alanine aminotransferase
ARC	Anticipated Event Review Committee
AST	aspartate aminotransferase
ALP	alkaline phosphatase
Breg	regulatory B cell
C _{max}	maximum observed serum concentration
C _{min}	minimum observed serum concentration
CMML	chronic myelomonocytic leukemia
COPD	chronic obstructive pulmonary disease
CR	complete response
CyTOF	cytometry by time of flight
eCRF	electronic case report form
eDC	electronic data capture
ECG	electrocardiogram
ECOG	Eastern Cooperative Oncology Group
EMA	European Medicines Agency
EOT	end-of-treatment
EPO	erythropoietin
ESA	Erythropoiesis-Stimulating Agent
FDA	Food and Drug Administration

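### Protocol 11.4 sets concentrations below quantification to zero and also plans geometric means, which become zero or not computable with a single such value

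*Protocol*

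**What the plan says.** Protocol Section 11.4 lists the planned summaries: "Descriptive statistics (geometric and arithmetic means, standard deviation, and coefficient of variation [%]) will be provided to summarize serum concentrations". They apply "at each sampling time point and PK parameters such as" Cmax and Cmin.

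The same section handles values below the quantification limit (BLQ) in two steps. They are flagged: "All concentrations below the lowest quantifiable concentration or missing data will be labeled as such in the concentration database". Then, for computation: "Concentrations below the lowest quantifiable concentration will be treated as zero in the summary statistics". The second sentence does not distinguish between arithmetic and geometric statistics. The section also requires the Clinical Study Report to document how many subjects and samples were excluded.

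Cmin is a predose value; it "is defined as the minimal concentration observed immediately before infusion". The BLQ rule therefore reaches the Cmin summary.

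The daratumumab pharmacokinetic schedule has predose and end-of-infusion samples on Day 1 of Cycles 1, 2, 3, 7 and 12, and follow-up samples "4 and 8 weeks after last dose of daratumumab". The Cycle 1 Day 1 predose sample precedes the first dose.

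The SAP lists characterisation of pharmacokinetics as a secondary objective (Section 2.2) but contains no section on how concentrations are analysed. SAP Section 3.6 limits summaries to subjects who received daratumumab, so only the daratumumab schedule matters here.

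**The concern.** Two sentences of one section cannot both be carried out. A geometric mean is defined for positive values; substituting zero makes it degenerate. The output table would show 0, or an empty or error cell, at any time point with one BLQ value, even if every other subject had a well-measured concentration.

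Whoever programs the table would then have to choose a workaround with the data in view. The possible workarounds give different answers, so the reported geometric mean would depend on an unplanned choice. Pharmacokinetic characterisation is a secondary objective. Protocol Section 11.3 also names pharmacokinetics among the results that gain weight if the primary outcome is inconclusive (6 or 7 responders).

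**Working it through.** The plan states no figure to reproduce here. The check has three parts: the definition, a numerical illustration, and where zeros can occur.

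**1. Definition.** For n concentrations x₁ … xₙ, GM = (x₁ × … × xₙ)^(1/n) = exp[(1/n) Σ log xᵢ]. If any xᵢ = 0, the product is 0 and GM = 0. In the log form, log 0 is undefined (minus infinity), so the mean log and the geometric SD cannot be computed. This holds for any n and any other values.

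**2. Illustration (assumed data).** Take n = 30, the planned arm size in Protocol Section 11.2. Draw 29 positive values from a log-normal distribution (assumed median 200, log-SD 0.6, arbitrary units) and add one BLQ value.

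| Handling of the one BLQ value | Geometric mean |
|---|---|
| Set to 0, as written | 0 (log form: not computable) |
| Left out (n = 29) | 191.1 |
| Half the limit, assumed limit 0.2 | 148.6 |
| Half the limit, assumed limit 1 | 156.7 |
| Half the limit, assumed limit 2 | 160.4 |

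For an assumed limit of 1: exp[(29 × log 191.1 + log 0.5)/30] = 156.7. Half-limit substitution is 16% (160.4/191.1 = 0.84) to 22% (148.6/191.1 = 0.78) below leaving the value out. The workable rules therefore disagree, which is why one has to be fixed in advance.

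The arithmetic statistics survive the zero: the mean goes from 212.6 to 212.6 × 29/30 = 205.5, with SD 96.4 and CV 96.4/205.5 = 46.9%.

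**3. Where zeros can arise.** The schedule has 5 predose, 5 end-of-infusion and 2 follow-up time points.

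- *Cycle 1 Day 1 predose.* No study drug has been given, so essentially every value is expected to be BLQ. The geometric mean fails by design. If all values are zero the arithmetic mean is 0 and CV% = SD/mean = 0/0 is undefined too.
- *Later predose samples and the two follow-up samples.* BLQ values are possible, for example after missed doses, which Protocol Section 6.3.5 does not allow to be made up, or during washout. The documents give no BLQ rate. With an assumed rate p and 30 independent samples, P(at least one BLQ) = 1 − (1 − p)³⁰:

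| Assumed p | P(at least one BLQ in 30) |
|---|---|
| 1% | 26% |
| 2% | 45% |
| 5% | 79% |
| 10% | 96% |

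The number of samples at later time points is not stated. Fewer than 30 would lower these figures.

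- *End of infusion (Cmax).* BLQ values are unlikely, so these summaries should be unaffected.

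**The case against.** The strongest reply is that little is lost. The one certain failure is at a sample taken before any drug, where a geometric mean carries no pharmacokinetic information under any rule. Elsewhere the failure is only possible: Protocol Section 3.3 describes a dose chosen for exposure consistent with target saturation, which does not suggest frequent BLQ values on treatment, though it does not exclude them. The percentages above rest wholly on assumed rates. Arithmetic means and SDs remain available, and any population pharmacokinetic analysis would follow its own plan. All of this stands, and it limits the size of the point. It does not make the two sentences compatible.

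A reader might also infer that software will silently drop the zeros, bias the geometric mean upward and leave no trace. The documents do not support that. No software is named, and the written rule gives a visible 0 or an empty cell, not a hidden bias. BLQ values must be labelled in the database, and exclusions must be documented in the Clinical Study Report. What remains is narrower. The exclusion count is not required by time point or by statistic. A value kept as zero for the arithmetic mean but left out of the geometric mean would not clearly count as an exclusion.

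The qualifier in Section 11.4 that parameters are summarised as appropriate sets no BLQ rule, so it does not rescue the text.

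**Conclusion.** The point holds as a minor error in the written plan. The zero rule and the planned geometric mean conflict at any time point with one BLQ value. The conflict is certain at Cycle 1 Day 1 predose, assuming no circulating daratumumab from earlier exposure. At later troughs, Cmin and the 4- and 8-week follow-up samples it is possible, with a probability that the documents do not allow one to calculate.

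The reach is descriptive pharmacokinetics only. It would be wrong to infer that the pharmacokinetic objective as a whole is compromised. End-of-infusion summaries should be untouched, arithmetic means and SDs stay computable, and CV% fails only when every value at a time point is zero. Nor does the point touch the primary analysis: the decision rule uses the number of responders alone, and the supporting role given to pharmacokinetics for an inconclusive result does not mention geometric means.

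**What to change.** Amend Protocol Section 11.4, or add a short pharmacokinetic paragraph to the SAP, to say:

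- BLQ values are set to zero for arithmetic statistics only.
- For geometric means, one prespecified rule applies. Half the quantification limit is an example. It is a convention whose result depends on the limit, so the limit should be stated with the table. Using quantifiable values only would also be computable, but it shifts the geometric mean upward and gives it a different denominator from the arithmetic mean beside it.
- The number and percent of BLQ values are shown at each time point.
- No geometric mean is given at the first predose sample or where most values are BLQ, and CV% is not given where the mean is zero. The exact cutoff for most is a matter of convention and should be written down.

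The cost is a sentence or two and a BLQ count in the concentration table. No new data are needed, because BLQ values are already labelled in the database.

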11.5. Immunogenicity Analyses

The incidence of anti-talacotuzumab and anti-daratumumab antibodies will be summarized for all subjects who receive at least 1 dose of talacotuzumab and daratumumab and have appropriate samples for detection of antibodies to talacotuzumab and daratumumab (ie, subjects with at least 1 sample obtained after their first dose of talacotuzumab and daratumumab). A listing of subjects positive for anti-talacotuzumab or anti-daratumumab antibodies will also be presented.

11.6. Biomarker Analyses

Biomarker measures and the change from baseline will be listed, tabulated, and plotted where appropriate. Subjects may be grouped by treatment, biomarker subgroups, or clinical response. Correlation of baseline or changes of biomarkers with clinical parameters will be analyzed by appropriate statistical methods (eg, parametric or non-parametric, univariate or multivariate).

Results of biomarker analyses may be presented in a separate report. Planned biomarker analyses may be deferred if emerging study data show no likelihood of providing useful scientific information.

11.7. Pharmacokinetic/Pharmacodynamic Analyses

If sufficient data are available, pharmacokinetic/pharmacodynamic modeling may be performed, including exploring the relationship between serum concentrations of talacotuzumab or daratumumab and biomarkers, PD markers, and endpoints of clinical efficacy and safety, and may include data from other studies. If these analyses are performed, the details and results will be presented in a separate report.

11.8. Safety Analyses

Safety analyses will be performed using the Treated Population. Safety will be evaluated using the NCI-CTCAE (Version 4.03). The safety parameters to be evaluated are the incidence, intensity, and type of adverse events, clinically significant changes in the subject's physical

examination findings, vital signs measurements, clinical laboratory results (hematology and chemistry), and deaths. Exposure to study treatment and reasons for discontinuation will be tabulated.

Adverse Events

Treatment-emergent adverse events are adverse events that occur after the first dose of study drug through 30 days following the last dose of study drug; any adverse event considered study drug-related regardless of the start date of the event; or any event that is present at baseline but worsens in severity or is subsequently considered drug-related by the investigator. Treatment-emergent adverse events will be summarized by System Organ Class and preferred term, by intensity (NCI-CTCAE, Version 4.03), and by drug relationship.

The verbatim terms used in the eCRF by investigators to identify adverse events will be coded using the Medical Dictionary for Regulatory Activities (MedDRA).

Clinical Laboratory Tests

Laboratory data will be summarized by type of laboratory test. Reference ranges and markedly abnormal results (specified in the Statistical Analysis Plan) will be included in the summary of laboratory data. Descriptive statistics will be calculated for each laboratory analyte at baseline.

Parameters with predefined NCI-CTCAE toxicity grades will be summarized. A summary of the shifts in selected laboratory hematology and serum chemistry parameters from baseline to the worst toxicity grade during the study will be provided. The worst toxicity grade during the study will be tabulated.

Electrocardiogram

Electrocardiogram data will be listed.

Vital Signs

Descriptive statistics of temperature, heart rate, and blood pressure (systolic and diastolic) values and changes from baseline will be summarized at each scheduled time point. The percentage of subjects with values beyond clinically important limits will be summarized.

11.9. Safety Review

A sponsor safety review committee will review all the safety data on a quarterly basis, or ad hoc, as needed. Committee members include study team clinicians and company safety officer.

12. ADVERSE EVENT REPORTING

Timely, accurate, and complete reporting and analysis of safety information from clinical studies are crucial for the protection of subjects, investigators, and the sponsor, and are mandated by regulatory agencies worldwide. The sponsor has established Standard Operating Procedures in conformity with regulatory requirements worldwide to ensure appropriate reporting of safety information; all clinical studies conducted by the sponsor or its affiliates will be conducted in accordance with those procedures.

Method of Detecting Adverse Events and Serious Adverse Events

Care will be taken not to introduce bias when detecting adverse events or serious adverse events. Open-ended and nonleading verbal questioning of the subject is the preferred method to inquire about adverse event occurrence. For some studies, subjects are not always able to provide valid verbal responses to open-ended questions. In these circumstances, caregivers or guardians would provide information regarding adverse event occurrence.

Solicited Adverse Events

Solicited adverse events are predefined local and systemic events for which the subject is specifically questioned.

12.1. Definitions

12.1.1. Adverse Event Definitions and Classifications

Adverse Event

An adverse event is any untoward medical occurrence in a clinical study subject administered a medicinal (investigational or non-investigational) product. An adverse event does not necessarily have a causal relationship with the treatment. An adverse event can therefore be any unfavorable and unintended sign (including an abnormal finding), symptom, or disease temporally associated with the use of a medicinal (investigational or non-investigational) product, whether or not related to that medicinal (investigational or non-investigational) product. (Definition per International Conference on Harmonisation [ICH]).

This includes any occurrence that is new in onset or aggravated in severity or frequency from the baseline condition, or abnormal results of diagnostic procedures, including laboratory test abnormalities.

Note: The sponsor collects adverse events starting with the signing of the ICF (refer to Section 12.3.1, All Adverse Events, for time of last adverse event recording).

Serious Adverse Event

A serious adverse event based on ICH and EU Guidelines on Pharmacovigilance for Medicinal Products for Human Use is any untoward medical occurrence that at any dose:

- Results in death
- Is life-threatening
(The subject was at risk of death at the time of the event. It does not refer to an event that hypothetically might have caused death if it were more severe.)
- Requires inpatient hospitalization or prolongation of existing hospitalization
- Results in persistent or significant disability/incapacity
- Is a congenital anomaly/birth defect
- Is a suspected transmission of any infectious agent via a medicinal product

- **Is Medically Important***

*Medical and scientific judgment should be exercised in deciding whether expedited reporting is also appropriate in other situations, such as important medical events that may not be immediately life threatening or result in death or hospitalization but may jeopardize the subject or may require intervention to prevent one of the other outcomes listed in the definition above. These should usually be considered serious.

If a serious and unexpected adverse event occurs for which there is evidence suggesting a causal relationship between the study drug and the event (eg, death from anaphylaxis), the event must be reported as a serious and unexpected suspected adverse reaction even if it is a component of the study endpoint (eg, all-cause mortality).

Unlisted (Unexpected) Adverse Event/Reference Safety Information

An adverse event is considered unlisted if the nature or severity is not consistent with the applicable product reference safety information. For talacotuzumab and daratumumab, the expectedness of an adverse event will be determined by whether or not it is listed in the Investigator's Brochure.

Adverse Event Associated With the Use of the Drug

An adverse event is considered associated with the use of the drug if the attribution is possible, probable, or very likely by the definitions listed in Section 12.1.2, Attribution Definitions.

